- 2. Assign each participant to one of the three treatment strategies of interest (see Table 1) based on their self-reported use of prescribed anti-migraine medications in the prior 30 days: participants who used lasmiditan at least once (Lasmiditan Group), participants who used another prescribed acute anti-migraine medication (includes, but is not limited to, triptans, ubrogepant [Ubrelvy], rimegepant [Nurtec], zavegepant [Zavzpret]; see Annex 3 for the complete list) at least once and did not use lasmiditan (Other Acute Medications Group), and participants who did not use any prescribed acute anti-migraine medication

(No Acute Medication Group). The self-reported use of prescribed preventive antimigraine medication will not be considered for treatment group classification.

- 3. Collect and record each participant's self-reported and calculated confounder history prior to their analytic 'time zero' (see Section 9.7 for potential confounders of interest).
- 4. Define follow-up for each participant from analytic 'time zero' until the earliest of the following: outcome event, loss to follow-up (day 67 of non-response, corresponding to non-response on two consecutive surveys), participant withdrawal, deviation from assigned treatment strategy (e.g., treatment switch), loss of eligibility, or administrative end of study (one-year of follow-up).
- 5. Generate a counting-process formatted dataset for this 'nested trial' derived from longitudinal treatment, outcome, and confounder information assessed in Steps 1-4 (see Section 9.7.2.2.2.1 for example data structure).
- 6. Repeat Steps 1-5 above for each sequential calendar day in which participants will be recruited into the survey study.
- 7. Bind all datasets produced in Step 5 by row. This will serve as the analytic dataset for the primary analysis (see Section 9.7.2.2.2.1 for example data structure).

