9.7.2.2.2 Primary Statistical Analysis

9.7.2.2.2.1 Data Structure and Notation

The data structure generated from the procedure illustrated in Section 9.1 will take on the general form shown in Table 5. As illustrated, each row of the data will represent an observation of a given participant at the kth interval of follow-up for the mth 'trial.' The treatment indicator A_k will take on one of three values corresponding to the treatment strategies of interest (see Section 9.1) and will be constant for a given participant within a given mth trial. Treatment history, denoted A_{k-1} , is the treatment the participant received in the prior (k-1) interval. A vector of baseline covariates, denoted L_0 , will take on fixed values across all 'k' intervals of a given participant's 'participation' in an mth trial. A vector of time-varying covariates, denoted L_k , will take on their recorded values at time 'k' in a given participant-trial. The event indicator, denoted D_{k+1} , will take on a value of one if the event occurred in the subsequent (k+1) interval, or a value of 0 otherwise (e.g., censoring).

In the data structure, the number of rows for each participant in a given mth trial will correspond to the length of follow-up. For example, in Table 5, Participant 3 participated in nested trial 7 and nested trial 9. This participant was followed-up for four intervals in trial 9 and experienced the outcome event in the 4th interval of follow-up. Notably, treatment information recorded in the 4th interval of follow-up is discarded because it is unknown whether treatment was administered before or after the outcome event within that interval. This is because the surveys only collect information and treatment data at the 30-day level.

Participant ID	Trial No. (m)	Follow -up (k)	Treatment (A _k)	Treat Hx (A _{k-1})	Baseline Covariate (L ₀)	Time- Varying Covariate (L _k)	Outcome (D _{m+k+1})	Censor (C _{m+k+1})
1	45	0	0	0	0	0	0	0
1	45	1	0	0	0	1	0	0
1	45	2	0	0	0	0	0	1
2	34	0	2	2	1	0	0	0
2	34	1	2	2	1	1	1	0
3	8	0	1	1	0	1	0	0
3	8	1	1	1	0	0	0	1
3	9	0	0	1	1	0	0	0
3	9	1	0	0	1	0	0	0
3	9	2	0	0	1	1	1	0

 Table 5.
 Generalised Longitudinal Data Structure for the Final Analysis

9.7.2.2.2.2 Statistical Models

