- 2. It may not be possible to achieve balance between all potential confounders across treatment groups (i.e., ASMD<0.1). Imbalances in baseline characteristics will be addressed with a re-specification of inverse probability weights (e.g., Changing the functional form of the variable or including interaction terms). However, if imbalances remain these will be described along with their potential impact on the outcome estimate(s).
- 3. It may not be possible to model all collected covariates due to sparsity, collinearity, or other factors that can preclude convergence of statistical models. For this reason, the final variables and functional forms of the baseline (L_0) and time-varying (\overline{L}_k) covariate vectors described in the models above will be determined at the time of analysis.
- 4. The time interval of the analysis, denoted 'k', directly influences the dimensionality of the dataset, and concequent computational intensity of the analysis. Particularly, choosing a time interval of one day will greatly increase the number of rows in the analytic data set and, concequently, increase the computation time of nonparametric bootstrap algorithms for standard error estimation. Therefore, if computation times are too great then the time interval of the analysis may be expanded accordingly (e.g., to one week or one month).

9.7.2.2.2.3 Missing Data

Missing data may arise from participants who skip a single survey only, or who are lost to followup (defined as non-responce on two concecutive follow-up surveys). Participants who are lost to follow-up will be censored at 67 days following the opening of their last survey (as participants are allotted 7 days to answer each 30-day survey). Missing data arising from non-response will be addressed using *last observation carried forward*, where the most recent survey responses are "carried forward" under the assumption that participants' treatment and confounder histories did not change during the time spanning from the participant's final response through the period of non-response.

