The survey will ask participants to consider their driving and migraine experience within the last 30 days and within the last 12 months at baseline; while the primary analysis depends on the relatively recent 30-day period, there remains the potential for recall bias, particularly for self-reported data within the last 12 months. In case of a collision, the longer the time elapsed since the collision, the more difficult it will be for the participants to recall. This may have an impact on their ability to accurately report circumstances and events occurring the hours proceeding the accident (e.g., accurately recall the timing of any accidents relative to when medications were last taken). To minimise recall bias in this study, participants will be administered follow-up surveys every 30 days, will be instructed to complete a survey in one sitting and guided to answer the questions in sequence. The questionnaires have been designed to collect only the information required for the analytic objectives to minimise recall burden. At baseline, a limited set of key variables will be collected for MVAs within the past 12 months to limit the burden on participants and improve response accuracy, and results for the 12-month period will be interpreted cautiously.

Because treatment and outcome variables are ascertained at the 30-day level, temporality between treatments and outcomes reported in the same interval cannot be established. For this reason, the primary statistical analysis is designed to estimate the hazard of experiencing a MVA in the *subsequent time interval* given treatment history *in the time interval prior* to the MVA. If a participant had in fact ceased using the treatment reported in the interval prior to the MVA, or begun an alternate treatment in the interval in which the accident was reported, then the participant's treatment status maybe misclassified. However, this misclassification bias is likely to be non-directional, resulting in a similar bias on the effect estimation between treatment groups.

Secondary objectives were specified to investigate the extent of treatment misclassification for this cause providing additional information on circumstances of MVA, including use of anti-migraine medication in the 24 hours prior to the accident.

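### Contingency 4 lets computing time set the follow-up interval k, and so decides whether the protocol's one-interval lag keeps drug use reported in the crash's own 30-day survey from counting as prior treatment

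*Protocol*

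**What the plan says.** In 9.7.2.2.2.1 the event indicator "will take on a value of one if the event occurred in the subsequent (k+1) interval", so treatment at k is paired with a crash one interval later and the width of k is the exposure-outcome lag. The section discards treatment recorded in the event's own interval because "it is unknown whether treatment was administered before or after the outcome event within that interval". It gives the reason: "This is because the surveys only collect information and treatment data at the 30-day level".

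9.9.2 makes the same argument: "Because treatment and outcome variables are ascertained at the 30-day level, temporality between treatments and outcomes reported in the same interval cannot be established". The primary model is therefore said to estimate the hazard in the following interval "given treatment history *in the time interval prior* to the MVA".

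Contingency 4 in 9.7.2.2.2.2 treats the width of k as a matter of data-set size. It warns that "choosing a time interval of one day will greatly increase the number of rows in the analytic data set", and then: "if computation times are too great then the time interval of the analysis may be expanded accordingly (e.g., to one week or one month". No other criterion for k is given.

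Three further facts bear on this. Follow-up surveys collect the dates of crashes, but migraine medication only as use over the past 30 days (9.3.4). Nested trials open daily: "Repeat Steps 1-5 above for each sequential calendar day in which participants will be recruited into the survey study" (9.1, step 6). Within a nested trial, treatment is constant and is set from reported use in the 30 days before time zero (9.7.2.2.2.1; 9.1, step 2).

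**The concern.** The rationale in 9.7.2.2.2.1 and 9.9.2 needs an interval as wide as the survey window. Contingency 4 allows a narrower one and widens it only when the bootstrap runs too slowly. With k of a day or a week, discarding the event interval removes only that day or week. The neighbouring days can carry the same undated 30-day answer, given on a survey completed after the crash.

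Three routes then open for information arising after the crash to be placed before it:

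- **Deviation censoring.** A switch first reported in the crash's survey has no date. If it is dated before the crash, follow-up ends there and the event is lost.
- **Weights.** Recent attacks, impact of migraine, miles driven and new comorbidities from the crash's survey can enter the treatment and censoring weights for days before the crash.
- **Trial opening.** A nested trial that opens inside the crash's survey window may have its treatment filled from the survey that closes later.

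At stake is whether the primary hazard ratio keeps the time order that 9.9.2 claims for it. The censoring weights would not be expected to repair the first route, because they condition on treatment and covariate history and not on the crash that prompted the change.

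**Working it through.** The protocol states no figure to reproduce here. The check asks how often a short k defeats the lag, and how large one route could be.

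**Inputs.** Twelve 30-day windows, hence 360 days of follow-up (9.3.4; Table 2, note a). Crash dates known, medication use undated within the window (9.3.4). About 3% of drivers crash per year (9.5). Assumption, because the protocol gives no rule: each analysis day takes its values from the survey covering it.

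**Step 1: how often the preceding interval touches the crash's own window.**

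- k = 1 day: only the first day of each window looks back to an earlier survey. (360 − 12)/360 = 348/360 = 96.7%.
- k = 7 days: the first 7 days have no earlier follow-up interval. At each later window start b = 30, 60, ..., 330, the previous week ended before the window for 7 − (b mod 7) days: 5, 3, 1, 6, 4, 2, 7, 5, 3, 1, 6, which sum to 43. (360 − 7 − 43)/360 = 310/360 = 86.1%. If the whole previous week must lie in that window, the share is 66.7%.
- k = 14 days: 70.6%.
- k = 30 days, aligned with the participant's survey windows: 0%.

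**Step 2: size of the censoring route alone.** Let the true hazard ratio be 1.0. Let q be the share of comparator crashes followed, in the same window, by a start of lasmiditan that is dated before the crash. Those events are censored out of the comparator. The person-time lost is negligible at 3% per year, so

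apparent HR = 1/(1 − q).

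- q = 5%: 1/0.95 = 1.05
- q = 10%: 1/0.90 = 1.11
- q = 20%: 1/0.80 = 1.25

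If instead a share q of lasmiditan crashes is lost, because use stops after the crash and the report shows none, the apparent HR is 1 − q: 0.95, 0.90 and 0.80. If use does not change after a crash, it is 1.00. The protocol gives no value for q.

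**Step 3: what a 30-day interval costs.** The event probability per 30 days is 1 − 0.97^(30/365.25) = 0.25%, or 0.50% at a hazard ratio of 2 (using 0.97² for the year). Both are far below the 8% limit that 9.7.2.2.2.2 sets for reading the odds ratio as a hazard ratio.

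A full-window lag does attenuate. Suppose the true hazard ratio for use in the crash's own window is 2, and 70% of users in one window use again in the next (assumed).

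- At 50% prevalence of use, 30% of prior non-users use now: (1 + 0.70)/(1 + 0.30) = 1.31.
- At 20% prevalence, 0.20 × 0.30/0.80 = 7.5% of prior non-users use now: 1.70/1.075 = 1.58.

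**The case against.** The strongest reply is that treatment cannot follow k at all. It is constant within a nested trial and fixed from the 30 days before time zero, and confounder history is taken before time zero (9.1, steps 2 and 3). This stands, and it limits the point. A reader might infer that with a short k the crash's own survey simply supplies the exposure, so that lasmiditan taken after a crash reclassifies comparator crashes as lasmiditan crashes. With equal-sized groups that would give (1 + q)/(1 − q), or about 1.1 to 1.5 for q of 5% to 20%. The documents do not support that reading: it describes an ordinary same-window comparison, not the planned one. Only the three routes listed above remain.

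Second, the protocol nowhere writes that k is 30 days. It speaks of the resolution of the surveys, and a one-day starting point is only implied by the word expanded. This is also correct. The conflict lies between the reason given for the lag and the rule that sets its width, not between two stated values of k.

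Third, the discard rule, read by its reason, could be taken to cover the whole survey window, and mapping reports to rows is ordinary SAP detail. The mapping may be. But the discard rule is written for the interval, and Contingency 4 states a criterion for that interval that ignores the survey window. An SAP that followed Contingency 4 could break 9.9.2.

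Fourth, a lag of a full window misclassifies a drug taken as needed. True, and a real cost. However, 9.9.2 already adopts the lag and accepts misclassification from it.

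**Conclusion.** The point holds as an internal conflict that should be resolved before analysis. The time-order safeguard in 9.7.2.2.2.1 and 9.9.2 works only when k is at least the survey window, and Contingency 4 makes that depend on run time.

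The shares of 96.7% and 86.1% show how often the safeguard is bypassed under the assumed day-assignment rule. They are not shares of biased crashes. The size of any bias rests on that unstated rule and on unknown behaviour after a crash. For the censoring route alone it is 1.05 to 1.25 with 5% to 20% of non-users starting after a crash. It lies below 1 if crashes deter use, and is nil if use is unchanged.

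For scale, Table 3 gives 1.29 to 3.10 around a hazard ratio of 2.00 at 1000 per group, a half-width of ln(3.10/1.29)/2 = 0.44 on the log scale. The largest illustrated shift, ln 1.25 = 0.22, is about half of that. More precision would not remove it.

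**What to change.** Reconcile 9.7.2.2.2.1, Contingency 4 and 9.9.2 in one of two ways:

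- Fix k in advance at the participant's own 30-day survey window. A calendar month that does not line up with the surveys is not enough. Use crash dates only to place the event in its window and to count person-time.
- Or keep a finer grid, and state that at any k the treatment, deviation status and time-varying covariates come only from a survey window that closed before the interval at risk. Apply the same rule to nested trials that open inside a window.

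In either case, remove computing time as the criterion for the lag.

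This is a change of wording, and the first option also reduces computing. Its costs are a coarser time scale, which matters little at about 0.25% events per 30 days, and attenuation from lagged exposure to an as-needed drug (a hazard ratio of 2 falling to 1.31 or 1.58 in the illustration above). 9.9.2 accepts part of this as misclassification. It should also say that the lag can pull a real effect towards the null.

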9.7.2.3 Additional Analyses

Additional analyses aiming to address secondary objectives will be conducted as part of the final analysis: 1) to describe migraine experience and reported use of prescribed anti-migraine medication among study treatment groups' participants (Lasmiditan Group, Other Acute Medication Group, and No Acute Medication Group) at baseline and during the follow-up period, and 2) to describe the circumstances of all MVAs self-reported during the study period, including migraine status, reported use of prescribed anti-migraine medication prior to MVA, preceding symptoms, and influence of alcohol or drugs at the time of the MVA, as well as severity of the accident and related injuries, among study treatment groups' participants (Lasmiditan Group, Other Acute Medication Group, and No Acute Medication Group).

Descriptive statistics will be used to summarise information collected for all enrolled participant at baseline and during the 12-months follow-up period and characterise migraine experience (age at first diagnosis, presence of aura, number of migraine attacks by month and impact on daily life) and reported use of prescribed anti-migraine medication (names of acute and preventive antimigraine medications, dosage for lasmiditan) among the three treatment groups, and according to demographics subgroups and other medical history. Details and circumstances of MVAs for which the participant was the driver will be descriptively summarised among the subgroup of participants who reported at least one MVA during the 12-month follow-up period and according to each treatment group (Lasmiditan Group, Other Acute Medication Group, and No Acute Medication Group).

Subgroup descriptive analyses to characterise circumstances of MVAs will be conducted by demographics and driving characteristics (type and duration of holding an active driver's licence, ZIP code of residency to classify urbanisation of area of residence, and approximate number of miles driven), number of self-reported MVAs during the observational period, perceived level of fault, severity of the accident (approximated by the extent of motor vehicle and/or property damages), speed of the motor vehicle driven by the participant, other vehicles and persons involved, and related injuries.

Subgroup analyses will use common descriptive statistics to summarise migraine attack at the time of MVA, use of prescribed anti-migraine medication up to 24 hours prior (acute and/or preventive, drug class, lasmiditan dosage and timing of administration in relation to the MVA), symptoms immediately preceding the accident, as well as potential mitigating factors (such as use of concomitant medication carrying a risk of MVA up to 24 hours prior, use of alcohol or drugs, environmental factors [i.e., time of the day, weather, visibility and lighting conditions]) (details in Section 9.3.4).

In addition, circumstances and details of MVAs will be described among subgroups of participants 1) having experienced at least one MVA during the study period and treated with lasmiditan in the 12-month study period, 2) treated with lasmiditan in the 30-day period prior to a self-reported MVA, 3) treated with lasmiditan in the 24-hour period prior to a self-reported MVA.

Complete details of the planned analyses will be documented in the SAP.

9.7.3 Benchmark Comparison

To our knowledge, no hazard ratio or incidence rate of MVA among migraine patients have been previously published in the literature. An unadjusted descriptive comparison of the annual incidence of self-reported MVAs in each of the study groups (among participants in Phase 2) relative to the rate observed for the general population will be provided, drawing on statistics from the National Highway Traffic Safety Administration including the annual Traffic Safety Facts report from where the annual national MVA rate will be extracted for the same or soonest year of study enrolment. The description will be presented by subgroups where possible, including by age group and sex.

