9.2.3 Rationale for Inclusion/Exclusion Criteria

Older drivers (aged 75 years or older) will not be recruited as they have been reported being at higher crash death rates than middle-aged drivers (aged 35 to 54). (Cicchino 2015) Age-related declines in vision and cognitive functioning as well as physical changes might also affect both their driving abilities (TRB 2004) and their ability to accurately complete the survey questions.

All participants will be required to have been issued their driver's licence at least 1 year before enrolment in order to capture baseline driving history. Additionally, this criterion will exclude novice drivers, who are known to be at higher risk of accidents (Ivers et al. 2009).

To be representative of the targeted populations, no exclusion will be made based on the number of accidents a participant has had prior to enrolment to the study, the number of miles a participant drove the year prior to enrolment, or the class of driver's licence possessed by the participants. Given these characteristics would potentially be associated with the risk of accidents, this information will be collected and incorporated into the statistical analysis.

For feasibility reasons and in order to ensure the representativeness of the targeted population, participants using preventive migraine medication will not be excluded. Nevertheless, self-reported use of preventive migraine medication will be collected and the data agreement with linked prescription data will be assessed at baseline and at the ed of follow-up period. Self-reported use of preventive migraine medication will be taken into account as a potential confounding factor in the main analysis (see Section 9.7.2.2) and subgroups descriptive analyses will be performed to describe participants' baseline characteristics and circumstances of MVAs. Assuming that over-the-counter (OTC) medications used to treat migraine attacks do not carry an excess risk of accident, and considering that it is not possible to assess the concordance between self-reported use of OTC medications and prescription data, no information regarding the use of non-prescribed anti-migraine medication will be collected and no exclusion is considered. Nevertheless, self-reported use of concomitant medication carrying a risk of MVA (including some OTC drugs) will be collected at baseline and at each follow-up survey (see Section 9.3.3 and Section 9.3.4).

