9.5 Study Size

According to the US Department of Transportation data through 2021 (US DOT [WWW]), approximately 3% of licenced drivers in the US have motor vehicle crashes during a year; therefore, approximately 3% of participants are expected to have an accident during the 12 months follow-up. This incidence rate is restricted to crashes involving either the car insurance or the police and might be slightly different than the incidence of MVAs self-reported by drivers.

Due to the lack of clear evidence for elevated incidence of MVAs in individuals with migraine compared to the general population, it is assumed that the incidence of MVAs in the general population can be expected in any of the comparison groups (3% per year). A sample of 793 participants per treatment group would provide 80% power at 5% level of significance for detection of a hazard ratio (HR) of 2.0. Given this is a safety study, no alpha correction method will be used. In order to achieve this sample size, an additional 20% will be targeted for enrolment in anticipation of participant dropout (992 per treatment group). A HR of 3.0 could be detected with a minimum of 397 participant after attrition, assuming an MVA rate of 3% in the lower risk group. Thus, a number of 1000 participants per treatment group, is targeted to be enrolled into the study. Due to a limited source population of lasmiditan-treated patients, challenges are anticipated for the recruitment of participants in the Lasmiditan Group.

If a sufficient number of participants treated with lasmiditan is enrolled, prospective follow-up and a comparative analysis will be executed as part of the final analysis (See Section 9.7.2.2).

If the required sample size is not achieved in the Lasmiditan Group and/or the number of incident MVA in the study period is insufficient to provide meaningful comparison between Lasmiditan Group and comparator groups (Other Acute Medication Group and No Acute Medication Group), unadjusted incidence rates of MVAs in each treatment group with precision estimates will be provided as primary analysis (see Section 9.7.2.2.2.2) and descriptive statistics will summarise participants characteristics, treatment patterns, driving patterns and self-reported MVAs experience through the 12-months of follow-up period.

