9.9.2 Information Bias

As with all collection of self-reported data, there is the possibility that participants may give inaccurate responses. For prescription anti-migraine medication, agreement between self-report and pharmaceutical claims data was notably higher when participants were asked to report 'current' use (kappa statistic 0.66, 95% confidence interval [CI] 0.23-1.00) relative to the results for a recall period of the past year (kappa statistic 0.36, 95% confidence interval [CI] 0.00-0.72). (Lacasse et al. 2016) Validation with pharmacy claims data will assess the internal data validity of self-reported prescription medication.

Sensitive data regarding MVAs are being collected in the study, including whether the accident was reported, the use of medications, drugs, or alcohol prior to the accident, and/or distracted driving, which could predispose participants to not answer truthfully due to the fear of judgment or embarrassment. For MVAs, there is evidence that self-reported data has poor test re-test reliability. (af Wåhlberg and Dorn 2015) The risk of social desirability bias may be mitigated by use of an anonymised online survey, combined with assurance on data privacy, compared to interview-based methods. This will be emphasised in the survey instructions to encourage accurate and truthful responses from participants. Moreover, participants will not be able to change answers once they are submitted and will not be contacted to clarify or revise responses at any point. If a participant reports illegal activities (i.e., taking illegal drugs or taking medications that are not allowed before driving), he will be aware that no action will be taken.

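### The benchmark in Section 9.7.3 compares all self-reported MVAs with a national rate that appears to count only police- or insurer-involved crashes, so the overall ratio can mislead in either direction

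*Protocol*

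**What the plan says.** **The comparison.** Setting MVA incidence in context against the US general population is a secondary objective (Protocol, Section 8). Section 9.7.3 plans "An unadjusted descriptive comparison of the annual incidence of self-reported MVAs in each of the study groups" relative to the general-population rate. The source is National Highway Traffic Safety Administration statistics, including "the annual Traffic Safety Facts report from where the annual national MVA rate will be extracted". On age and sex it adds: "The description will be presented by subgroups where possible, including by age group and sex".

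**The national rate.** Section 9.5 states that "approximately 3% of licenced drivers in the US have motor vehicle crashes during a year", citing US Department of Transportation data. The reference list (Section 13) identifies that source as the Traffic Safety Facts annual report tables. Section 9.5 then qualifies the figure: "This incidence rate is restricted to crashes involving either the car insurance or the police and might be slightly different than the incidence of MVAs" that drivers report themselves. It gives neither the direction nor the size of the difference.

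**The study event.** Table 1 defines the outcome as the first self-reported MVA with the participant driving. It sets no threshold for police, insurer or severity.

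**Report status.** Section 9.9.2 says sensitive MVA data are collected, "including whether the accident was reported". It does not say reported to whom, and the variable lists in Sections 9.3.3 and 9.3.4 contain no such item.

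**Population.** Section 9.2.3 says of the one-year licence requirement that "this criterion will exclude novice drivers, who are known to be at higher risk of accidents". It also explains why drivers aged 75 or older are not recruited.

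**The concern.** A ratio of two incidences can be read only if both count the same kind of event. Here the study side counts any accident the driver chooses to call an MVA, while the national side, on the protocol's own description, counts only those that came to the police or an insurer. A scrape in a car park that nobody reports enters one side and not the other. Section 9.7.3 neither restricts the study numerator nor carries over the warning from Section 9.5, and the limitations in Section 9.9 do not discuss the benchmark.

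At stake is a stated secondary objective of a safety study whose reports go to regulators. Section 9.5 expects difficulty in recruiting lasmiditan users. If the comparative analysis is not feasible, unadjusted incidence rates by group become the primary analysis, and Section 9.7.3 is the only planned external reference for them. A ratio above or below 1 could then be taken as a finding about migraine patients or lasmiditan users when it reflects the definition of the event.

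**Working it through.** **1. The protocol's own figures.** The 3% is the working rate for the design. At HR 2.0 the lasmiditan risk is 1 − 0.97² = 5.91%, shown as 5.9% in Table 3. A two-proportion calculation (3% vs 5.9%, two-sided 5%, 80% power, pooled variance under the null, no continuity correction) gives 793 per group. With 20% dropout, 793 / 0.8 = 991.25, rounded up to 992. Both match Section 9.5.

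**2. Effect of the definition alone.** Suppose participants have exactly the national rate of police- or insurer-involved crashes. Let r be the share of self-reported MVAs that reach police or insurer. No document gives r, so a range is shown.

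- National hazard: −ln(1 − 0.03) = 0.03046 per year.
- Self-reported hazard: 0.03046 / r.
- Self-reported one-year risk: 1 − exp(−0.03046 / r).
- Apparent ratio: that risk / 3%.

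| r (assumed) | Self-reported risk | Apparent ratio | Expected events, n = 1000 | Exact 95% CI at that count | Chance the CI lies wholly above 3% |
|---|---|---|---|---|---|
| 1.0 | 3.0% | 1.00 | 30 | 2.03% to 4.26% | 2% |
| 0.9 | 3.3% | 1.11 | 33 | 2.28% to 4.60% | 8% |
| 0.7 | 4.3% | 1.42 | 43 | 3.13% to 5.75% | 56% |
| 0.5 | 5.9% | 1.97 | 59 | 4.52% to 7.54% | 99% |

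Simple division gives nearly the same: 3% / 0.9 = 3.33%, 3% / 0.7 = 4.29% and 3% / 0.5 = 6.0%, for ratios of 1.11, 1.43 and 2.00. The intervals are Clopper-Pearson and assume 1000 participants with complete one-year follow-up. With 793, the chances in the last column become 2%, 6%, 44% and 97%. Section 9.7.3 plans no test against 3%; that column only shows how easily an artefact could look like a signal.

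**3. Forces in the other direction.** Let c be the factor by which the study's count falls short of a like-for-like count. The ratio is then roughly c / r, so a shortfall can cancel or reverse the excess. With r = 0.7, c = 0.7 gives 1.0, and any c below 0.7 gives a ratio below 1. The documents give three reasons for c below 1:

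- novice drivers, described as higher risk, are excluded (Section 9.2.3);
- participants may not answer truthfully, and self-reported MVAs have poor test-retest reliability (Section 9.9.2); the first of these would lower the count;
- a severe accident may go unreported, which Section 9.9.5 says could lead to underestimation, mitigated in part by the alternative contact.

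None comes with a number, so c is as unknown as r.

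**4. Matching the event.** If the study numerator is limited to MVAs involving police or insurer, r = 1 by definition and the expected ratio from the definition alone returns to 1.00. The effect of age-sex standardisation cannot be computed, because the documents give no age- or sex-specific rates.

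**The case against.** The strongest reply is that this is a descriptive secondary output offered as a frame of reference. No test or decision depends on it, the protocol has already admitted the limitation in Section 9.5 and expects the difference to be slight, and details belong in the SAP. Part of this stands: the consequence is limited to how one output is read. But the numerator and the unadjusted overall comparison are fixed in Section 9.7.3 itself, and the caveat stands only in the sample-size section.

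A reader might also infer more than the documents support:

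- **That age and sex are ignored.** Section 9.7.3 plans strata where possible. What is missing is a standardised overall figure; strata do not repair the event definition.
- **That a false excess is the expected result.** The net direction is unknown (step 3 of the working), and the ratios of 1.1 to 2.0 follow wholly from the assumed r.
- **That excluding drivers aged 75 or older is shown to lower the study's accident rate.** Section 9.2.3 cites higher crash death rates and possible effects on driving ability. Only novice drivers are called higher risk for accidents.
- **That a matched numerator is already in hand.** Section 9.9.2 mentions report status in general terms, and the variable lists name no police or insurer item.
- **That the primary comparison is compromised, or that the benchmark would be the only comparison left if it is dropped.** The between-group hazard ratio does not use the national rate. In the fallback, all three groups are still reported on the same self-reported outcome.

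Finally, Section 9.5 states the restriction for its 3%. Applying it to Section 9.7.3 rests on the shared report family. That is a sound inference, but Section 9.7.3 does not say it, and it allows for other statistics from the same agency.

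**Conclusion.** The point holds in a limited form. As written, Section 9.7.3 sets a broader event against a narrower one for a stated secondary objective, without standardising the overall comparison and without the caveat that the protocol gives elsewhere. The overall ratio can therefore mislead, and its direction cannot be known from the documents. Under the assumption that 90%, 70% or 50% of self-reported MVAs reach police or insurer, and with nothing pulling the other way, the definition alone would produce a ratio of about 1.1, 1.4 or 2.0 with no true excess. This rests on the 3% rate, on the assumed share, and on the benchmark in Section 9.7.3 carrying the same restriction as the figure in Section 9.5. The between-group hazard ratio is untouched. The change is worth making because it is cheap and removes the definitional mismatch.

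**What to change.** In Section 9.7.3:

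1. Base the benchmark ratio on MVAs that the participant says were reported to police or insurance. List that item explicitly in Sections 9.3.3 and 9.3.4.
2. Show all-MVA incidence beside it, without a ratio.
3. Where national age- and sex-specific rates are available, add an age-sex standardised observed/expected figure with an exact 95% CI for each group, besides the planned strata.
4. Repeat the caveat from Section 9.5.

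If the survey item cannot identify police or insurer involvement, report the rates side by side with the caveat and no ratio.

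**Cost.** If the item already separates police and insurer, the change is wording plus one table; if not, either the survey changes or the fallback applies. The statistical price is fewer events and a wider interval. With the assumed r = 0.7 and 1000 per group, about 43 events fall to 30, and the upper-to-lower limit ratio rises from 5.75 / 3.13 = 1.84 to 4.26 / 2.03 = 2.10.
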